10.14. Appendix 14: Abbreviations

The following is a list of abbreviations that may be used in the protocol.

Abbreviation	Term
AE	adverse event
Abs	absolute
ADA	anti-drug antibody
ADL	activities of daily living
AESI	adverse event of special interest
ALT	alanine aminotransferase
ApoB100	apolipoprotein B100
ANOVA	analysis of variance
AST	aspartate aminotransferase
ASTCT	American Society for Transplantation and Cellular Therapy
AUC	area under the curve
AUC ₁₆₈	area under the concentration-time curve from time 0 to 168 hours
AUC _{inf}	area under the concentration-time curve from time 0 to infinity
AUC _{last}	area under the concentration-time curve from time 0 to the time of the last quantifiable concentration
AUMC	area under the first moment plasma concentration curve
Bb	activated factor B
BBS	Biospecimen Banking System
BiPAP	bilevel positive airway pressure
BMI	body mass index
BP	blood pressure
BPM	beats per minute
BRC	Benefit Risk Committee
BUN	blood urea nitrogen
C1q	Complement component 1q
C3a	Complement 3a
C5a	Complement 5a
C _{av}	average concentration
CA	Competent Authority
CDC	complement-dependent cytotoxicity
CDS	core data sheet
C _{eff}	efficacious concentration
CFR	Code of Federal Regulations
CHO	Chinese Hamster Ovary
CI	confidence interval
CIA	Collagen-Induced Arthritis
CIDP	chronic inflammatory demyelinating polyneuropathy
CK	creatinine kinase
CKD-EPI	Chronic Kidney Disease Epidemiology Collaboration
CL	clearance
CL/F	apparent clearance
C _{max}	peak or maximum observed concentration
CO ₂	carbon dioxide (bicarbonate)
COVID-19	Corona virus disease 2019
CPAP	continuous positive airway pressure
CRF	case report form
CRO	contract research organization
CRS	cytokine release syndrome

Abbreviation	Term
CSA	clinical study agreement
CSF	cerebrospinal fluid
CSR	clinical study report
CT	Clinical Trial
CTA	clinical trial application
CTC	Common Terminology Criteria
CTCAE	Common Terminology Criteria for Adverse Events
CTFG	Clinical Trials Facilitation and co-ordination Group
CTMS	Clinical Trial Management System
CV	cardiovascular
DAI	Dosing Administration Instructions
DCT	data collection tool
DILI	drug-induced liver injury
DMC	data monitoring committee
DNA	deoxyribonucleic acid
DOI	duration of infusion
EAN	experimental autoimmune neuritis
EC	ethics committee
ECG	electrocardiogram
eCRF	electronic CRF
EDCMS	electronic data capture and management system
EDMC	external data monitoring committee
EDP	exposure during pregnancy
EDR	Extemporaneous Dispensing Record
EDTA	edetic acid (ethylenediaminetetraacetic acid)
eGFR	estimated glomerular filtration rate
EIU	exposure in utero
EMA	European Medicines Agency
EOI	end of infusion
ERB	external review board
ET	Early termination
EU	European Union
EudraCT	European Clinical Trials Database
FcγRs	Fcγ receptors
FDA	Food and Drug Administration (United States)
FDAAA	Food and Drug Administration Amendments Act (United States)
FFPE	formalin-fixed paraffin-embedded
FIH	first-in-human
FSH	follicle-stimulating hormone
GCP	Good Clinical Practice
GGT	gamma-glutamyl transferase
GLP	Good Laboratory Practices
hCG	human chorionic gonadotropin
HDL	high density lipoprotein
HDL-C	high density lipoprotein cholesterol
HCVAb	hepatitis C antibody
HepBsAg	hepatitis B surface antigen
HepBcAb	hepatitis B core antibody
HIPAA	Health Insurance Portability and Accountability Act
HIV	human immunodeficiency virus
HP	Healthy participant
HR	heart rate

Abbreviation	Term
Hr	hour
HRT	hormone replacement therapy
HSV-1	Herpes Simplex Virus 1
HSV-2	Herpes Simplex Virus 2
IB	investigators brochure
iC3b	inactive product of complement component 3b
ICD	Informed consent document
ICE	IGIV-C CIDP efficacy
ICH	International Conference on Harmonisation
ID	Identification
IEC	independent ethics committee
IgA	Immunoglobulin A
IgG	Immunoglobulin G
IgG2	Immunoglobulin G2
IND	investigational new drug application
INR	international normalized ratio
IFN γ	Interferon gamma
IL-1RA	Interleukin-1 receptor antagonist
IL-6	Interleukin-6
IP	investigational product
IRB	institutional review board
IRC	internal review committee
IRT	interactive response technology
ISR	infusion site reaction
ITP	idiopathic thrombocytopenic purpura or immune thrombocytopenia
IUD	intrauterine device
IUS	Intrauterine system
IV	intravenous
IVIg	intravenous immunoglobulin
IWR	interactive Web-based response
K ₂ EDTA	dipotassium ethylene diamine tetraacetic acid
LDL	low density lipoprotein
LDL-C	low density lipoprotein-cholesterol
LFT	liver function test
LOEL	lowest observed effect level
LPD	local product document
MCH	Mean corpuscular hemoglobin
MCHC	Mean corpuscular hemoglobin concentration
MCV	Mean corpuscular volume
MHRA	Medicines and Healthcare products Regulatory Agency
mDC	myeloid dendritic cells
MedDRA	medical Dictionary for Regulatory Activities
MRT	mean residence time
MTD	maximum tolerated dose
N/A	not applicable
ND	Not done
NHP	non-human primate
NK	natural killer
NOAEL	no observed adverse effect level
NOEL	no observed effect level
NSAID	non-steroidal anti-inflammatory drug
PACL	protocol administration clarification letter

Abbreviation	Term
PCV	premature ventricular complexes
PD	Pharmacodynamics
PE	physical examination
PEOI	prior to end of infusion
PG	Pharmacogenomics
PI	principal investigator
PK	Pharmacokinetics
PT	prothrombin time
PTT	partial thromboplastin time
QC	quality control
QTc	corrected QT
QW	weekly
RBC	red blood cell
RMC	Risk Management Committee
RNA	ribonucleic acid
SAD	single ascending dose
SAE	serious adverse event
SAP	Statistical Analysis Plan
SARS-CoV-2	severe acute respiratory syndrome coronavirus 2
SC	subcutaneous
SC Ig	Subcutaneous immunoglobulin
SCr	serum creatinine
SGOT	serum glutamic oxaloacetic transaminase
SGPT	serum glutamic pyruvic transaminase
SoA	Schedule of Activities
SOP	standard operating procedure
SPC	summary of product characteristics
SRSD	single reference safety document
SToD	Study team on demand
SUSAR	suspected unexpected serious adverse reactions
$t_{1/2}$	terminal half-life
T3	triiodothyronine
T4	thyroxine
TB	tuberculosis
Tbili	total bilirubin
TCC	total cell count
TG	triglycerides
T_{max}	time to reach maximum concentration
TNF- α	Tumor necrosis factor alpha
THC	tetrahydrocannabinol
TPN	Total parenteral nutrition
TSAb	Thyroid stimulating antibodies
TSH	Thyroid stimulating hormone
UA	urinalysis
ULN	upper limit of normal
US	United States
USPI	United States prescribing information
V_{ss}	volumes of distribution at steady-state
V_z	volume of distribution
V_z/F	apparent volume of distribution
WBC	white blood cell
WOCBP	Woman of child bearing potential

2. INTRODUCTION

PF-06755347 is a recombinant human IgG1 multimeric Fc fusion protein which includes the IgG1 hinge region, the CH2, and CH3 domains, with a human IgG2 hinge domain fused onto the C terminus. The molecule is designed to form Fc multimers, in order to enhance avidity to Fc γ receptors (Fc γ Rs).

The current study is the first clinical trial proposed with PF-06755347. It is designed to evaluate the safety, tolerability, pharmacokinetics (PK), as well as potential pharmacodynamic (PD) effect of PF-06755347 following single intravenous (IV) doses of PF-06755347 to healthy adult subjects.

2.1. Study Design

This is a Phase I, randomized, double-blind (Investigator and subject-blind, sponsor-open), placebo-controlled, parallel, single-ascending dose study of PF-06755347 in healthy subjects, to be conducted at a Pfizer Clinical Research Unit (CRU) that is in very close proximity to a major medical center. Personnel, trained in advanced cardiac life support, emergency resuscitative equipment and the management of anaphylaxis, are immediately available to treat systemic reactions under the supervision of a physician. IV fluids, epinephrine, antihistamine and methylprednisolone will be available for immediate parenteral use in the event of an anaphylactic reaction. In addition, a dedicated ambulance will be present at the research unit during dosing to facilitate rapid transfer to the Emergency Department of a major medical center, if needed.

The study will include 8 planned cohorts, with a provisional ninth cohort optionally added to explore or enhance the understanding of the full dose range. An optional Japanese cohort (Cohort 10) is also included. The optional Cohort 9 and Cohort 10 may or may not be conducted pending evaluation of available safety and PK data from other cohorts and at the discretion of the Sponsor.

[figure not shown]
A total of approximately 73 healthy adult subjects are planned to be randomized. Fewer subjects (N=5, 3 active and 2 placebo) are planned for Cohorts 1-3, which are expected to have plasma exposure below the predicted efficacious concentration range (ie, doses ≤ 1 mg/kg). For Cohorts 4-9 with expected plasma exposure near or exceeding predicted efficacious concentration range (ie, doses > 1 mg/kg), a total of 9 subjects (6 active and 3 placebo) is planned. If pharmacological activity or exposure is significantly greater than expected, the sample size for Cohorts 1-3 may be increased to 9 subjects at the discretion of the Sponsor in consultation with the PI. A total of 4 active subjects are planned for the optional Japanese cohort. A schematic of the overall study design is provided in [Figure 1](#).

The subjects within each cohort (except for the Japanese cohort) will be dosed using a sentinel dosing strategy with sequential block design (diagramed in Figure 1). Each cohort will consist of 2 or 3 blocks, depending on the cohort sample size, with a monitoring period of at least 72 hours between the dosing initiation in consecutive blocks. The number of subjects will increase sequentially, from 1 active and 1 placebo for the first block to 2 active and 1 placebo for the second block and 3 active and 1 placebo for the third block. For Cohorts 1-3, only the first and second blocks will be employed. The progression of dosing to the next block will occur if the dose is determined to be safe and well tolerated in the previous block by the PI. This sentinel dosing scheme will not be applied to the Japanese cohort, as the dose for this cohort, if conducted, will be a dose less than or equivalent to a dose studied in previous cohorts and deemed safe and well tolerated.

Screening evaluation will occur within 28 days prior to dosing. Eligible subjects who meet the entry criteria will be admitted into the CRU on Day -1 and are required to stay overnight through completion of Day 8 evaluations. Subjects will then return for outpatient visits per the Schedule of Activities through approximately Day 36 (≤ 1 mg/kg dose level) or Day 71 (> 1 mg/kg dose level) for a total of approximately 5 or 10 weeks study participation, respectively from first dose to follow-up, excluding screening. The follow-up period may be extended for a cohort block if any subject in the particular cohort block tests positive for anti-drug antibody to PF-06755347 at the scheduled follow-up visit, or has detectable concentration of PF-06755347 at final follow-up visit.

If a subject discontinues during the trial, the subject may be replaced at the discretion of the Sponsor in consultation with the PI. Doses in the dose escalation sequence may be repeated or adjusted depending on the results obtained during the study to explore different doses and/or infusion/dosing rates as needed. The total number of cohorts including the optional Japanese cohort will not exceed 10.

Figure 1 Sample Study Schematic

2.2. Study Objectives

2.2.1. Primary Objectives

- *To evaluate safety and tolerability of single IV escalating doses of PF-06755347 in healthy adult subjects.*

2.2.2. Secondary Objectives

- *To characterize the plasma PK profile of PF-06755347 following single ascending IV infusions in healthy adult subjects.*
- *To evaluate the immunogenicity profile of PF-06755347 following single ascending IV infusions in healthy adult subjects.*

CCI [REDACTED]

[REDACTED]

[REDACTED]

3. INTERIM ANALYSES, FINAL ANALYSES AND UNBLINDING

Safety and pharmacokinetic (PK) data will be reviewed after each cohort.

This is a sponsor open study, with the investigators and subjects blinded to study treatment. Specific Pfizer personnel (e.g. analytical staff, medical monitor, clinician, statistician, and clinical pharmacologist) will be unblinded to subject treatments in order to permit real-time interpretation of the safety and pharmacokinetic data, and to provide information necessary to potentially alter the dose escalation sequence. To minimize the potential for bias, treatment randomization information will be kept confidential by Pfizer personnel and will not be released to the investigator/study staff until the conclusion of the study. Unblinding will not be performed until the final database has been locked for all cohorts. Final analysis will follow the official database release.

4. HYPOTHESES AND DECISION RULES

4.1. Statistical Hypotheses

No hypotheses are required.

4.2. Statistical Decision Rules

No decision rules are required.

5. ANALYSIS SETS

5.1. Full Analysis Set

In general, the full analysis set is comprised of all randomized subjects. This population of subjects is not applicable for this study. Analysis sets for PK, safety and CCI data are defined in Sections 5.2, 5.4 and 5.5.

5.2. Pharmacokinetic Analysis Set

5.2.1. Concentration Analysis Set

The PK concentration population is defined as randomized subjects who received at least one dose and have at least 1 concentration.

5.2.2. Parameter Analysis Set

The PK parameter analysis population is defined as all randomized subjects who received at least one dose and have at least 1 of the PK parameters of interest.

5.3. Pharmacodynamic Analysis Set

The PD analysis population is defined as all randomized subjects treated who have at least one PD assessment in at least one cohort.

5.4. Safety Analysis Set

All subjects who receive at least 1 dose of study medication will be included in the safety analyses and listings.

5.5. Other Analysis Sets

CCI

5.6. Treatment Misallocations

All analyses will be performed on an “as-treated” basis and will not include data from subjects who are randomized but not treated.

If a subject takes a treatment that is not consistent with the treatment they are randomized to then they will be reported under the treatment that they actually receive for all safety, PK and CCI where applicable.

5.7. Protocol Deviations

Subjects who experience events that may affect their PK profile (eg dosing error) may be excluded from the PK analysis. At the discretion of the pharmacokineticist a concentration value may also be excluded if the deviation in sampling time is of sufficient concern or if the concentration is anomalous for any other reason.

A full list of protocol deviations will be compiled and reviewed to identify major and minor deviations prior to database closure.

5.7.1. Deviations Assessed Prior to Randomization

At screening, the investigator will assess subjects against the inclusion and exclusion criteria as set out in Sections 4.1 and 4.2 of the protocol.

5.7.2. Deviations Assessed Post-Randomization

Any significant deviation from the protocol will be reviewed prior to database closure and a decision taken regarding evaluation for each analysis population.

6. ENDPOINTS AND COVARIATES

6.1. Efficacy Endpoint(s)

None.

6.2. Safety Endpoints

In this section, the safety endpoints that will be measured during the study are detailed. Where applicable, details of the endpoints to be derived and definition of baseline are also provided.

The following data are considered in standard safety summaries (see protocol for collection days and list of parameters):

- adverse events;
- laboratory data;
- vital signs data;
- ECG and telemetry results.

6.2.1. Adverse Events

Any events occurring following start of treatment or increasing in severity will be counted as treatment emergent.

Events that occur in a non-treatment period (for example, washout or follow-up) will be counted as treatment emergent and attributed to the previous treatment taken.

6.2.2. Laboratory Safety Tests

Safety laboratory tests will be performed as described in the protocol.

To determine if there are any clinically significant laboratory abnormalities, the haematological, clinical chemistry (serum) and urinalysis safety tests will be assessed against the criteria specified in the sponsor reporting standards. The assessment will take into account whether each subject's baseline test result is within or outside the laboratory reference range for the particular laboratory parameter.

Baseline will be defined as the measurement on Day -1, or the last available pre-dose collection time point (whichever occurs later).

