2.3. Benefit/Risk Assessment

PF-06755347 is not expected to provide any clinical benefit to healthy participants but it may provide a transient increase in platelet count in participants with persistent or chronic ITP. This study is designed primarily to generate safety, tolerability, and pharmacokinetic data that will support further clinical development.

PF-06755347 has been shown to cause transient elevation in pro-inflammatory cytokines. Symptoms associated with CRS vary greatly and may be difficult to distinguish from other conditions. The more common symptoms include fever, nausea, headache, tachycardia, hypotension, rash and shortness of breath. The severity of symptoms can be mild to life threatening and thus there should be a high suspicion for CRS if these symptoms occur. Cytokines will be analyzed to determine if cytokine elevation consistent with CRS is observed (see [Section 10.10](#)). The severity of CRS will be assessed according to the most

recent consensus grading from the American Society for Transplantation and Cellular Therapy (ASTCT).²

For study participants with ITP, there is an increased risk of procedure-related bleeding/bruising from subcutaneous injections, mitigated by the lower bound of platelets in the eligibility criteria. An increased risk of thrombosis has also been reported in ITP.¹⁵ High dose single IV administration of PF-06755347 may transiently lower platelet counts in healthy participants, while repeat IV administration in non-clinical studies may also lower platelet counts. The predicted C_{max} with SC administration in ITP participants is approximately 6 fold lower than observed C_{max} at 1 mg/kg at which the reduction in platelet count was observed in healthy participant (see [Table 6](#)). More detailed information about the known and expected benefits and risks and reasonably expected adverse events of PF-06755347 may be found in the investigators brochure, which is the SRSD for this study.

Each study site should have a COVID-19 risk mitigation policy (RMP), which documents the site's COVID-19 virus testing strategy for participants and staff, social distancing measures, and management of COVID-19-like symptoms.

To account for the widespread deployment of COVID-19 vaccine during the COVID-19 pandemic, the benefit/risk analysis has assessed both the impact of PF-06755347 on risk of COVID-19 disease in study participants who may become infected with SARS-CoV-2 and the efficacy of COVID-19 vaccines.

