5.3. Inclusion Criteria for Participants with ITP

1. Male and female participants ages 18-55 years at time of ICD signature. Female participants may be of non-childbearing or childbearing potential.
2. Diagnosis of Primary ITP. ITP must be diagnosed in accordance with established guidelines.^{17,18}
 - Persistent (>3 months and ≤ 12 months) OR Chronic (>12 months).

AND

- Platelet count 30-75 x 10⁹/L (inclusive) with criteria achieved on 2 qualifying counts
 - The first platelet count must be taken within approximately 10 days prior to dosing. The second platelet count must be taken at the time of admission.
 - There must be at least 5 days between the 2 platelet counts
- 3. Participants must have received and responded to IVIg or corticosteroids as treatment for ITP (response is defined as achievement of platelet count >50 x 10⁹/L and doubling of platelet count from baseline).
- 4. Willing and able to comply with all scheduled visits, treatment plan, lab tests, lifestyle considerations and other study procedures.
- 5. BMI of 17.5 to 30.5 kg/m² and a total body weight >40 kg (88 lbs).
- 6. Capable of giving informed consent, including compliance with requirements and restrictions in ICD and in the protocol.

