6.6. Dose Progression

The participants within each cohort will be dosed using a sequential dosing scheme. For all cohorts, a single participant will be dosed at a given time, followed by a minimum of 72-hour (for IV) and 96-hours (for SC) safety monitoring period. In total there will be a minimum of 96 hours between each IV participant dosed and 120 hours for each SC participant dosed.

The following rules will be applied when considering dosing of the next participant in the cohort.

Sequential dosing may **proceed** only if no adverse events are reported OR all of the following criteria are met:

1. Any pro-inflammatory events are < Grade 2 Per CTCAE criteria in [Appendix 9](#).
2. All other adverse events are deemed mild or moderate in severity, regardless of relatedness.
3. Any laboratory, ECG or vital sign changes are considered not clinically significant.
4. No other pause or stop criteria are met.
5. For participants with ITP, in addition to the above criteria, no participant has greater than a 30% decrease in platelet count – defined from the immediate pre-dosing platelet count to the lowest postdosing platelet count. Dose progression will be independent of dose progression from HP cohorts at higher dose levels.

Sequential dosing should be **paused** if any criterion below is met in a participant receiving active drug:

1. Grade 2 (Objective) pro-inflammatory event (vomiting, diarrhea, hypotension or hypoxia) (see [Appendix 9](#)).
2. Adverse event which is considered to be severe (Grade 3 or higher) AND is deemed related to study intervention.
3. A moderate event (Grade 2) AND is deemed related to study intervention not otherwise identified as a proinflammatory event or AE of special interest, that in the opinion of the PI and Sponsor are of concern and warrant further investigation before additional dosing.
4. For participants with ITP, platelet count of <30 x 10⁹/L AND a decrease from baseline ≥30%, or a platelet count decrease from baseline of ≥50%, defined from the immediate pre-dosing platelet count to the lowest post-dosing platelet count, or a bleeding or bruising-related AE CTCAE 4.03 Grade 2 or higher (except metrorrhagia Grade 3 or higher).

Sequential dosing should be **stopped** at the current dose level if any criterion below is met in participant receiving active drug:

1. Grade 3 or greater pro-inflammatory event.
2. Serious adverse event that is deemed related to study intervention.

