8.3.5. Laboratory Data

Laboratory data will be listed and summarized by treatment, which will be reported separately for Cohort 10 (if applicable) in accordance with the sponsor reporting standards. Baseline is as defined in [Section 6.2.2](#).

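### The SAP derives no lowest platelet count or maximum percentage fall per participant, so its planned tables may not show how often platelets fell, by dose and against placebo

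*SAP*

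**What the plan says.** **The signal.** Protocol 2.3 states that a high single intravenous dose "may transiently lower platelet counts in healthy participants", and refers to 1 mg/kg as the dose where this was seen.

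**How the protocol measures it.** Protocol 6.6 gives platelet rules for ITP participants only. They use 30% and 50% decreases, "defined from the immediate pre-dosing platelet count to the lowest postdosing platelet count".

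**How the SAP handles laboratory data.** Under SAP 6.2.2, haematology, chemistry and urinalysis "will be assessed against the criteria specified in the sponsor reporting standards", with account taken of whether the "baseline test result is within or outside the laboratory reference range for the particular laboratory parameter". The baseline is one value: "Baseline will be defined as the measurement on Day -1, or the last available pre-dose collection time point", whichever is later. SAP 8.3.5 adds only this: "Laboratory data will be listed and summarized by treatment".

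**How the SAP handles other safety data.** SAP 6.2.3 derives each subject's largest increase and decrease in vital signs, and 6.2.4 the largest value and increase for ECG parameters. Appendix 1 sets categories for them, and 8.3.6 and 8.3.7 tabulate numbers and percentages of subjects. No laboratory parameter has an equivalent derivation or category.

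**The concern.** Safety is the primary objective, and platelet reduction is a laboratory effect that the protocol says has already been seen in healthy participants. Those cohorts contain the study's only placebo control. The natural summary of a brief fall is each person's lowest count relative to baseline, and protocol 6.6 uses that measure in ITP. The SAP does not compute it.

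The study could therefore finish with every count on file and still have no planned table showing how many participants at each dose, and how many on placebo, lost a given share of their platelets. The ITP cohorts have no placebo, so a healthy-participant table on the same scale would be a useful reference for them.

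**Working it through.** The plan states no figure to reproduce. The check asks which falls would escape a cut tied to the lower limit of normal (LLN).

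**Inputs from the documents:** reporting thresholds of 30% and 50% (protocol 6.6, where they bind in ITP only); one pre-dose baseline (SAP 6.2.2).

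**Assumptions, not in the documents:** LLN of 130 to 150 x 10^9/L; cut C = k x LLN with k = 1, 0.75 or 0.5; healthy baselines normal with mean 220 to 280 and SD 40 to 55, truncated to 150-400.

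**Formula.** A fall f from baseline B leaves (1 - f)B. It is not below the cut when B is at least C/(1 - f).

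- LLN 150, k = 1: 150/0.7 = 214 for a 30% fall; 150/0.5 = 300 for a 50% fall.
- LLN 130, k = 1: 130/0.7 = 186; 130/0.5 = 260.
- LLN 150, k = 0.75 (cut 112.5): 161 and 225.
- LLN 150, k = 0.5 (cut 75): 107 and 150.

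**Share of falls not flagged, LLN 150, over the assumed baselines:**

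| Cut | 30% fall | 50% fall |
|---|---|---|
| LLN | 58-95% | 2-35% |
| 0.75 x LLN | 96-100% | 47-92% |
| 0.5 x LLN | essentially all | essentially all |

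Example with mean 250, SD 55 and cut 150: the share of baselines at or above 214 is 0.77, and at or above 300 is 0.19. A percentage-change table counts all such falls by construction.

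**Which baseline?** The haematology rows, as far as the extracted tables can be read, show no sample at 0 h on Day 1. The SAP baseline is then in practice the admission count, which is also the count available for the protocol 6.6 rule. ITP eligibility supplies a second count ("There must be at least 5 days between the 2 platelet counts"), so averaging the two was checked.

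- Independent fluctuation with variance s^2: change from one count has variance 2s^2, and from the mean of two 1.5s^2. The SD ratio is sqrt(0.75) = 0.866, about 13% smaller.
- Serial correlation c(d) = exp(-d/tau), counts L = 5 or 9 days apart, visit t days after dosing: the single-count variance is proportional to 2 - 2c(t+1), and the mean-of-two variance to 1 + (1 + c(L))/2 - c(t+1) - c(t+1+L).
- Eight days after dosing, the SD ratio is 0.88-0.90 (tau 3 days), about 1.00 (14 days) and 1.04-1.06 (30 days).
- One day after dosing, it is 1.01-1.37 for tau of 3 to 30 days.

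Averaging is therefore a trade-off and gives no dependable gain.

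**Chance falls.** A lowest count over many visits falls by chance alone. In a simulation of ITP participants with no drug effect and 13 independent post-dose counts, the share with at least one count more than 30% below the single baseline was 4.1%, 24%, 43% and 56% for an assumed within-person CV of 10%, 15%, 20% and 25%. The table needs placebo beside it, and an uncontrolled ITP row cannot by itself be read as a drug effect.

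**The case against.** **The cut-off is unseen.** The sponsor criteria are outside the documents, and SAP 6.2.2 says only that baseline range status is considered. A reader might infer that the SAP applies a plain reference-range cut. It does not say so, and a percentage rule in the sponsor standard is not excluded. This stands, and it makes the conclusion conditional.

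**The thresholds belong to ITP.** A reader might infer that the protocol acts on 30% to 50% falls in healthy men. It does not: laboratory changes in them are judged for clinical significance, and a move from 250 to 175 need not qualify. This stands. The thresholds are useful here only as reporting points.

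**Nothing is hidden.** All counts are listed, protocol 9.8 has abnormalities of potential concern described, and healthy cohorts have about 4 to 8 people. This is true, but a listing is not a planned frequency by dose against placebo. A reader might add that by-visit means would dilute a brief fall; SAP 8.3.5 does not specify that format.

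**The signal is intravenous.** Protocol 2.1 ends intravenous dosing, and 2.3 predicts a subcutaneous peak concentration in ITP about 6 times lower than that at 1 mg/kg. This limits the expected hazard. The intravenous data must still be reported, and the same table would show whether the subcutaneous cohorts are free of the effect.

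**ITP.** A reader might fault the SAP because every ITP baseline (30-75 x 10^9/L by eligibility) would be out of range under any LLN above 75, or because a single-count baseline is needlessly variable. The SAP covers healthy subjects given intravenous doses and plans no ITP analysis, so neither can be charged to it. The single count also agrees with protocol 6.6.

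**Conclusion.** The point holds in a limited form. The SAP gives platelets no per-participant lowest count, maximum percentage fall or category, although it does the equivalent for vital signs and ECG and the protocol reports an observed platelet effect. Whether falls go uncounted depends on sponsor criteria that cannot be seen. If the cut is a multiple of the lower limit of normal, the share missed runs from 2% (50% falls, cut at the limit) to essentially all (cut at half the limit), under the assumed limit of 150 and the assumed baselines. That range is too wide to serve as an estimate; it shows only that a range-based cut cannot be relied on to count such falls. No hypothesis test is affected. What is missing is a planned incidence summary for a known effect under the primary safety objective. The documents do not support replacing the single pre-dose baseline.

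**What to change.** 1. **SAP 6.2.2:** derive each participant's lowest post-dose platelet count and maximum percentage decrease from the existing single pre-dose baseline. Include planned and unplanned post-dose counts, as 8.3.6 and 8.3.7 do for vital signs and ECG.
2. **SAP 8.3.5:** tabulate n (%) with decreases of at least 30% and at least 50% by treatment, with placebo alongside. State that these are descriptive reporting thresholds and carry no decision rule.
3. **Sponsor criteria:** if they already contain a percentage-change rule for platelets, cite it in 6.2.2 and align the table with it.
4. **ITP:** when the SAP is extended to those cohorts, show them separately and keep the single pre-dose count as primary baseline. The mean of the two qualifying counts may be an optional sensitivity analysis; it would require the first qualifying count to be in the database.

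Leave the rules in protocol 6.6 unchanged.

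The cost is a few lines of SAP text, a short derivation and one small table. The main table uses counts already scheduled. Protocol 9.4 has the SAP finalised before database lock, so the change fits the planned timing.
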